**Collaborating Institutions Co-Investigators:**

[name], PhD

College of Dentistry, University of Florida

St. Jude Children's Research  
Hospital [name]  
Place  
[name]  
[contact]

**Protocol MNEMONIC and Title: Prevention/Treatment of Oral Mucositis in Children and Adolescents undergoing Hematopoietic Cell Transplant (HCT) using Photobiomodulation Therapy (PBM)**

**Principal Investigator:** [name], RN

**IND Holder:** Not Applicable

**Brief Overview:** Oral mucositis is a significant and common toxicity experienced by patients who receive chemotherapy as a preparatory regimen for a hematopoietic cell transplant (HCT). Furthermore, oral mucositis has been reported as the single most debilitating side effect reported by patients undergoing HCT. The incidence of HCT mucositis among adults is estimated to range between 76% and 89%; however, comparisons are difficult due to variability in patient ages, treatments and criteria for scoring oral mucositis.

The use of intra-oral photobiomodulation (PBM) therapy in adult patients after the development of oral mucositis is well documented and now included in the international mucositis guidelines, with limited evidence in pediatrics. This study will build evidence for the incorporation of extra-oral PBM therapy into daily nursing care of children and adolescents undergoing HCT. This intervention has potential in providing evidence for efficacy in the prevention and treatment of oral mucositis, the single most debilitating side effect reported by patients undergoing HCT.

Patients admitted for an allogeneic hematopoietic cell transplant (HCT) will be eligible to receive daily extra-oral and intra/oral PBM beginning on the first morning of conditioning chemotherapy and continuing until Day +20 or engraftment (ANC  $\geq$  500 for two consecutive days), at which time treatment will end. Patients admitted for an autologous transplant and determined by the transplant team to be at risk for  $\geq$  grade 3 oral mucositis will be eligible to receive daily extra-oral/intra oral PBM beginning on the first morning of conditioning chemotherapy and continuing until engraftment (ANC  $\geq$  500 for two consecutive days) or until patient is without mucositis (grade 1) for two consecutive days.

**Intervention:** PBM is defined as the application of coherent or non-coherent light to an area of pathology to promote tissue regeneration, reduce inflammation, and relieve pain. The biological mechanism of PBM allows intracellular absorption of energy by intracellular organelles and molecules; however, the amount and specifics of energy absorption is dependent upon the wavelength and rate of energy delivery dependent on the power of the device. PBM is FDA approved for tissue damage, pain and inflammation. There is no age limitation.

**Brief Outline of Treatment Plan:** Children, adolescents and young adults admitted for an allogeneic HCT and those determined by the transplant team to be at risk for  $\geq$  grade 3 oral mucositis will be eligible to receive PBM (34 x 660 nm 10 mW, 35 x 850 nm 30 mW; 1390 mW total power output at an irradiance of 50mW/cm^2). The PBM will be administered by trained research staff beginning on the first morning of the conditioning regimen (plus/minus 2 days) and continue daily until Day +20 or engraftment (event occurring first) and for allogeneic continue daily until engraftment or until the patient is

Protocol MNEMONIC and Title: Prevention/Treatment of Oral Mucositis in Children and Adolescents undergoing Hematopoietic Cell Transplant (HCT) using Photobiomodulation Therapy (PBM)
without grade 1 (no) mucositis for two consecutive days. All patients will receive the standard mouth care regimen prescribed for transplant patients. The nurse, advance nurse practitioner and physician caring for the patient will grade mucositis daily per the Common Toxicity Criteria (version5), and pain will be documented per institutional pain assessment scale (0-10). Patient- reported pain, and oral function will be collected daily.
Study Design: This two-stage design study will assess for development of grade 3 mucositis during daily PBM treatment.
Sample Size: 66
Data Management: Data management and statistical analysis will be provided by the Division of Nursing Research and Biostatistics Department at St. Jude Children's Research Hospital
Human Subjects: The risks to subject are minimal. Retinal irritation is unlikely; however, each patient will be issued glasses for eye protection. Patients will be informed of this during informed consent discussion. Adverse events will be monitored and reported and treated appropriately.

## 1.0 OBJECTIVES

The use of intra-oral photobiomodulation therapy (PBM) in adult patients, who develop therapy related mucositis, is included in the international mucositis guidelines, with limited evidence in pediatrics. This intervention has the potential of providing additional evidence within the pediatric literature to the benefits of PBM in the prevention and treatment of oral mucositis in pediatric patients undergoing HCT. The ultimate goal would be incorporation of PBM into daily nursing care guidelines for pediatric patients undergoing HCT, thus improving outcomes and health-related quality of life.

### 1.1 Primary Objective

*To evaluate feasibility and efficacy of photobiomodulation therapy (PBM) in reducing oral mucositis in children and adolescents at risk for grade 3 oral mucositis undergoing an allogeneic hematopoietic cell transplant (HCT).*

Hypothesis 1: Children and adolescents will receive 75% of the attempted PMB treatment and will be less likely to develop grade 3 oral mucositis from the 1st day of conditioning to day +20 transplant or engraftment (event occurring first)

### 1.2 Secondary Objectives

*To compare clinical manifestations associated with the development of oral mucositis between those treated with daily PBM and a matched control. Clinical factors to include: grade and duration of oral mucositis.*

Hypothesis 2: Children and adolescents treated with extra-oral PBM will develop lower grade mucositis, with shorter mucositis duration (days) than the comparison matched control.

### 1.3 Exploratory Objective

1. *To evaluate efficacy of photobiomodulation therapy in autologous patients at risk for grade 3 oral mucositis compared to matched control.*

Hypothesis: Children and adolescents treated with PBM will be less likely to develop grade 3 mucositis than matched control.

2. *To evaluate utilization of play-based procedural preparation and treatment feasibility and parental satisfaction.*

Hypothesis: Children and adolescents introduced to low level light therapy through play-based procedural preparation will complete treatment at all sites compared to those without play-based preparation.

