#### **3.3 Research Participant Recruitment and Screening**

Potential participants undergoing HCT will be identified in the weekly bone marrow pre-admission conference. Each participant being admitted for an allogenic transplant and meeting inclusion criteria will be offered PBM therapy. The bone marrow transplant clinicians may identify autologous recipient at risk for grade 3 mucositis per conditioning regimen or history of high-grade mucositis. These participants will be included for the exploratory objective. For all patients meeting inclusion criteria, an appointment will be made with the participant and family during the HCT evaluation period. The potential participant and parents will be approached by a member of the study team who will briefly explain the

study and respond to any patient/family questions. An educational slide show presentation delivered by an ipad will describe the PBM process and mechanism (see attached). At that time, the patient and parents will be asked if they wish to participate in the study. If they agree, the informed consent/assent document will be reviewed and signed. This meeting will take place approximately one week to day of admission to in-patient Transplant Service. All patients who meet the study criteria will be approached for enrollment.

After low level light therapy consent, participants will be offered the opportunity to receive a play-based preparation by a certified child life specialist (CCLS). Those who elect to receive this child life preparation will be scheduled to meet with a trained CCLS prior to admission. The play-based preparation will incorporate age and developmentally appropriate explanations of the non-invasive procedure and will be adapted to each patient's psychosocial and cognitive developmental needs. To standardize the child life preparation, the following components will be included in each of the interventions: hands on manipulation of the LLLT equipment (ie. Glasses and light tool), demonstration and return demonstration of procedure on a medical doll, and discussion and development of coping plan for procedure. The play-based preparation intervention will last approximately 30 minutes.

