Feasibility will be assessed similar to Treister et al [20] through the number of successful treatments administered by the total number of attempted treatments, providing the percentage of successful treatment administered. Daily treatment will include 6 sites of PBM application, with application documented as receiving all 6 applications, in part treatment (at least one to five sites) or no treatment. A successful treatment is defined as the treatment is successfully administered to 4 or more sites. Reasons for partial or no treatment will be documented. Criteria for feasibility is that the percentage of successful treatments administered exceeds 75%. The collected data will be summarized for total days on protocol, days treatment is received, cumulative dose and the number of treatments received at each site.

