**To evaluate utilization of play-based procedural preparation and treatment feasibility and parental satisfaction.**

Descriptive statistics (counts, percentages, mean, median, standard deviation and interquartile range) and confidence interval will be calculated for the percentage of successful treatment administered, total days on the protocol, days treatment is received, cumulative dose and the number of treatments received at each site between those who had procedural based preparation and those that did not. Descriptive statistics (counts, percentages, mean, median,) will describe parental satisfaction.

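### The play-preparation hypothesis concerns treatment at all six sites, but the planned summaries omit the all-six rate, and the self-selected groups are compared without adjustment

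*Combined protocol and SAP*

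**What the plan says.** The second exploratory hypothesis in 1.3 is that children introduced to the light therapy through play "will complete treatment at all sites compared to those without play-based preparation". It does not say whether completion is judged per session or per child.

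Section 4.1 sets six application sites per daily treatment, "with application documented as receiving all 6 applications, in part treatment (at least one to five sites) or no treatment". It then gives the success rule: "A successful treatment is defined as the treatment is successfully administered to 4 or more sites". Overall feasibility requires more than 75% of attempted treatments to be successful.

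For the play-preparation objective, 10.2.3 plans descriptive statistics, and a "confidence interval will be calculated for the percentage of successful treatment administered". The same is planned for days on protocol, days treated, cumulative dose and treatment counts per site, all "between those who had procedural based preparation and those that did not". No test, adjustment or stratification is given.

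Under 3.3 preparation is offered to participants after consent, and uptake is by choice: "Those who elect to receive this child life preparation will be scheduled to meet with a trained CCLS prior to admission".

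**The concern.** There are two separate problems.

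- **Outcome.** The hypothesis sets the bar at six of six sites, and the only completion percentage that 10.2.3 lists sets it at four of six. If preparation mainly turns four- or five-site sessions into six-site sessions, that percentage cannot register it. The all-six rate could be worked out later, but unless it is named in advance the choice of measure is left until the data have been seen.
- **Comparability.** Families choose the preparation. Those who accept and those who decline may differ in ways that affect cooperation, and the comparison is crude. A difference could appear without any effect of preparation, or a real effect could be masked.

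At stake is whether the reported summaries speak directly to the stated hypothesis, and how a reader would interpret a difference between the groups.

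**Working it through.** The plan gives no sample size, effect size, group split or test for this objective, so there is no figure to reproduce. All rates below are assumptions chosen for illustration. Only the six sites, the four-site rule and the patient numbers come from the documents.

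**1. How the two measures respond.** Let each site be completed independently with probability q. Then P(all six) = q⁶, and P(success) is the sum over k = 4, 5, 6 of C(6,k)·qᵏ·(1−q)⁶⁻ᵏ.

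| q | Success (≥4 of 6) | All six | Mean sites, 6q |
|---|---|---|---|
| 0.80 | 90.1% | 26.2% | 4.80 |
| 0.90 | 98.4% | 53.1% | 5.40 |
| 0.98 | about 100% | 88.6% | 5.88 |

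From 0.90 to 0.98, success moves by under 2 points and all-six by 88.6 − 53.1 = 35.5 points. From 0.80 to 0.90, the moves are 8.3 and 26.9 points.

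**2. What dose and per-site counts add.** Section 4.1 defines cumulative dose as proportional to the number of sites treated, so it follows the mean number of sites. From 0.90 to 0.98 that is 5.88/5.40 = 1.09, a rise of about 9%. These measures do move.

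They do not fix the all-six rate. If every site is completed in 90% of sessions, the all-six rate is lowest when missed sites never coincide, 1 − 6 × 0.10 = 40%, and highest when they always coincide, 90%.

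A second example takes both groups at 90% success, with all-six rates of 70% (prepared) and 50% (unprepared). The other 10% of sessions are counted as zero sites.

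- Partial sessions all at five sites: prepared 0.7×6 + 0.2×5 = 5.2; unprepared 0.5×6 + 0.4×5 = 5.0. The difference is 0.2 sites per session.
- Partial sessions all at four sites: 0.7×6 + 0.2×4 = 5.0 against 0.5×6 + 0.4×4 = 4.6. The difference is 0.4.
- Prepared partials at four, unprepared partials at five: 5.0 against 0.5×6 + 0.4×5 = 5.0. The difference is zero.

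So the gap usually shows in dose and counts, and vanishes only in a special pattern.

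Both measures are also totals over days. Under 4.1 treatment length depends on engraftment, and the stopping rules differ between allogeneic and autologous patients. A group difference in totals can therefore reflect duration. Days treated is listed too, so a per-day average can be formed, but an average number of sites is still not the all-six rate.

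**3. Self-selection with no true effect.** Let half the children be cooperative (all-six 80%) and half not (50%), with preparation changing nothing.

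- Uptake 40% in cooperative and 80% in uncooperative children: the cooperative share is 0.20/0.60 = 1/3 among prepared and 0.30/0.40 = 3/4 among unprepared. All-six is 60.0% against 72.5%, a difference of −12.5 points.
- Uptake 80% and 40%: the cooperative shares are 2/3 and 1/4. All-six is 70.0% against 57.5%, a difference of +12.5 points.

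**4. Precision.** Suppose all-six completion were compared as one yes/no per patient, 60% against 80%, two-sided 0.05. Power = Φ[(0.20 − 1.96·SE₀)/SE₁], with SE₀ from the pooled proportion and SE₁ unpooled. With 66 patients split equally, SE₀ = √(2×0.7×0.3/33) = 0.113 and SE₁ = √((0.24 + 0.16)/33) = 0.110, so power is 42%. Across uptake of 50% to 80%, power is about 35–42% with the 66 allogeneic patients (4.1) and 43–54% with 88, that is 66 plus the 22 expected autologous patients (10.2.3).

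**The case against.** The strongest reply is that the analysis does not rest on the four-of-six percentage. A child who skips the same two sites every day scores 100% on success and 0% on all-six, but also shows zero in two site columns and 4/6 = 67% of full dose on treated days. The treatment table in 4.1 is laid out by case, so a child completed all sites on every treated day exactly when all six counts equal the days treated. The daily all-six, partial or none record gives the session rate. The stated objective also mentions treatment feasibility, which 4.1 defines by the four-site rule, so reporting that percentage by group is legitimate. Finally, no passage says that uptake or cooperation varies with age, and age adjustment would not remove selection on anxiety or temperament.

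All of this stands. It rules out two inferences that a reader might draw: that a gap in all-six completion would go unseen, and that the trial cannot answer its own question. The other listed measures would usually move, and the outcome can be derived from data already collected.

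What remains is narrower. No listed summary is the all-six rate, group totals do not determine it, and the plan takes no account of who chose preparation.

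**Conclusion.** The point holds as a minor one. The hypothesis is about all sites, and the summaries listed in 10.2.3 approach it only indirectly. The success percentage is insensitive to the change of interest: under 2 points against about 35 in the first illustration, and none at all if preparation only moves four- or five-site sessions to six. Those sizes rest on assumed completion rates and, in the first case, on independent sites.

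The unadjusted comparison of self-selected groups could be wrong in either direction, by 12.5 points in the assumed example. A reader might infer that the groups will differ in age and that age would explain any difference. The documents do not establish this. It is plausible, since 3.1 sets no age limit and 3.3 adapts the preparation to developmental level, but it remains an assumption.

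The consequence is limited. The objective is exploratory and descriptive, has no decision rule, and nothing primary or secondary depends on it.

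**What to change.** In 10.2.3, under the play-preparation objective:

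- Add the percentage of attempted sessions with all six sites treated, taken from the daily record in 4.1, by preparation group. Calculate it for each patient and then summarise across patients, so that repeated sessions in one child are not treated as independent. State that unit in the hypothesis as well.
- Keep the success percentage, dose and per-site counts as supporting summaries.
- Show the all-six result by age group, with bands fixed in advance, or adjusted for age. Age is already abstracted under 6.2.
- Report baseline differences between those who chose and those who declined preparation, and label the comparison non-causal. Age adjustment deals with age only.
- Present estimates with confidence intervals rather than a test, given the low power shown above.

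The cost is a short paragraph of text and a little extra analysis, with no new data. The drawback is that age strata will be small when about 88 patients are also divided by an unknown uptake.

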## 2.0 BACKGROUND AND RATIONALE

### 2.1 Background

Oral mucositis is a significant and common toxicity experienced by patients who receive high-dose chemotherapy as a preparatory regimen for a hematopoietic cell transplant (HCT). Furthermore, oral mucositis has been reported as the single most debilitating side effect reported by patients undergoing transplantation.[1] The incidence of HCT conditioning mucositis is estimated to range between 76% and 89%; however, comparisons are difficult due to variability in patient ages, treatments and criteria for scoring oral mucositis.[2, 3]

Oral mucositis is a progressive process that begins shortly after the administration of high-dose chemotherapy and results from DNA strand breaks that result in direct cellular injury of cells in the basal epithelium and within the submucosa resulting in mucosal destruction.[2] Additionally, mucositis represents local tissue reactions including damage from reactive oxygen species, inflammatory cytokines, and damage to submucosa connective tissues and vasculature. Stages of oral mucositis include mucosal burning, erythema, edema with progression to ulceration. Ulceration occurs most commonly on the nonkeratinized mucosa of the mouth floor, tongue, buccal mucosa and soft palate.[3] Oral mucositis is noted several days after completion of chemotherapy with a peak in severity between 6 and 12 days post-transplant.[4]

Oral ulcerations are painful, may become secondarily infected, bleed and impact nutritional intake. Together these factors increase the need for parenteral nutrition, opioid administration for pain and predispose the patient to secondary infection and bacteremia. The cost of oral mucositis can be excessive due to increased utilization of antibiotics, blood products, pain medication and supplemental nutrition thus leading to longer hospitalizations. According to Sonis et al.,[5] a one point increase in peak mucositis grade in HCT has been associated with a 2.1 fold increase in risk of significant infection, 2.7 additional days of parenteral nutrition, 2.6 additional days of hospitalization, additional hospital cost of \$25,405 and 3.9 fold increase in risk of mortality with the first 100 days. While reporting benefit, the literature is limited in describing the efficacy of treatment for oral mucositis prevention and treatment among pediatric patients. Most studies have reviewed the efficacy of adult HCT oral mucositis interventions, with the inclusion of laser therapy recommended in adult oral mucositis guidelines.[2] Currently there is insufficient evidence for the application of PBM inclusion into oral mucositis guideline in the pediatric oncology population.[6]

This is a nurse led innovation utilizing a novel therapy for the prevention and treatment of the single most debilitating side effect reported in patients undergoing HCT. This innovative proposal has the potential to change our established Nursing Standard of Oral Care Guidelines for children and

adolescents undergoing a HCT through planned and coordinated application of daily PBM with standard oral care. If the PBM is found to reduce the severity and duration of oral mucositis, the change in nursing routine with the inclusion of nurse delivered PBM will have a direct impact on improving health outcomes specifically patient reported pain, decrease in positive blood and oral cultures and less days of nutritional support. A decrease in the severity and duration of oral mucositis will also have a potential impact on health care cost with a decrease in supportive care measures, which may subsequently decrease days of hospitalization.

## 2.2 Rationale for Photobiomodulation Therapy

PBM is defined as the application of coherent light to an area of pathology to promote tissue regeneration, reduce inflammation, and relieve pain. The biological mechanism of PBM allows intracellular absorption of energy by intracellular organelles and molecules; however, the amount and specifics of energy absorption is dependent upon laser wavelength and rate of energy delivery dependent on the power of the laser.[7] Mitochondria in stressed or ischemic tissues produces excessive mitochondrial nitric oxide (mtNO) which binds to cytochrome c oxidase, competitively displacing oxygen and consequently reducing ATP, but this inhibition of mitochondrial respiration significantly increases production of ROS (free radicals). These excess ROS trigger the process of inflammation, cell death and subsequently oral mucositis. Light of the correct wavelength (generated by low intensity lasers and LED's), when applied to stressed tissues, is absorbed by cytochrome c oxidase. The light displaces the mtNO thereby reducing oxidative stress and increasing ATP production; this reduces inflammation and increases cell metabolism. A recent comprehensive review described the mechanisms of action for light therapy and molecular interactions and the implication of cytochrome c oxidase as the photo acceptor modulating light therapy.[8]

Figure 1 demonstrates the stages of wound healing and the benefit of light stimulation.[8]

[figure not shown]

Figure 1 Wound healing stages light therapy is cited to act upon

Figure 2 illustrates possible excitatory pathway by which light stimulates the electron transport chain to higher functionality[8]

[figure not shown]

Figure 2 Effects of light therapy on the mitochondrial electron transport chain. Cytochrome c is stimulated to switch redox states, transferring electrons to cytochrome c oxidase at a higher rate, increasing proton transport and subsequently the mitochondrial membrane potential. Increase in hydrogen ion gradient drives ATP synthase to increase ATP catalysis. Electron transport follows decreased energy states (\*\*\*\*), while electron leakage reduces oxygen to reactive oxygen species (— · —)

Several studies have evaluated the effect of PBM on prevention and treatment of oral mucositis among adult patients undergoing HCT, with encouraging results. [9-11] These results prompted a change in the latest update of the Multinational Association of Supportive Care in Cancer and International Society of Oral Oncology (MASCC/ISO) mucositis guidelines and now include a new recommendation for the use of PBM (34 x 660 nm 10 mW, 35 x 850 nm 30 mW; 1390 mW total power output at an irradiance of 50mW/cm^2), in prevention of adult

patients receiving HCT conditioned with high-dose chemotherapy, with or without total body irradiation .[12] The guideline also suggested the use of PBM in the prevention of oral mucositis in head & neck cancer patients treated with radiation therapy without concomitant chemotherapy.

